7.10	Handling of Missing Data, Outliers, Visit Windows, and Other Information	34
7.10.1	Missing Data	34
7.10.2	Outliers	34
7.10.3	Visit Windows	34
8	DOCUMENT REVISION HISTORY	36
9	REFERENCES	36
10	APPENDICES	37
10.1	Appendix 1: Key Contributors and Approvers	37

I. LIST OF ABBREVIATIONS AND KEY TERMS

List of Abbreviations

Abbreviations	Description of abbreviations
ALP	Alkaline phosphatase
ALT	Alanine aminotransferase (GPT)
ANCOVA	Analysis of Covariance
AST	Aspartate aminotransferase (GOT)
BP	Blood pressure
BPH	Benign prostatic hypertrophy
BUN	Blood urea nitrogen
CK	Creatinine kinase
CSR	Clinical Study Report
ECG	Electrocardiogram
FAS	Full Analysis Set
HUS	hours of undisturbed sleep
ICH	International Conference on Harmonization of Technical Requirements for Registration of Pharmaceuticals for Human Use
IPSS	International Prostate Symptom Score
IRT	Interactive Response Technology
ISN	International study number
MedDRA	Medical Dictionary for Regulatory Activities
MMRM	Mixed Model Repeated Measure
OAB	Overactive Bladder
OAB-q	Overactive Bladder questionnaire
OABSS	Overactive Bladder Symptom Score
PD	Protocol deviation
PK	Pharmacokinetic(s)
PPS	Per Protocol Set
PR	Pulse rate
PSA	Prostate-specific antigen
PVR	Post-void residual (volume)
Q1	1 st Quartile, 25 th Percentile
Q3	3 rd Quartile, 75 th Percentile
Qave	Average flow rate
Qmax	Maximum urine flow rate
QoL	Quality of Life
QTcF interval	QT interval, corrected for heart rate according to Fridericia's formula
SAF	Safety Analysis Set
SAP	Statistical Analysis Plan
SD	Standard deviation
TEAE	Treatment-emergent adverse event
TLF	Tables, Listings and Figures
Total HRQL score	Total Health-Related Quality of Life score
UFM	Uroflowmetry

Abbreviations	Description of abbreviations
ULN	Upper limit of normal
WHO-DD	World Health Organization Drug Dictionary

List of Key Terms

Terms	Definition of terms
Adverse event	Any untoward medical occurrence in a subject administered a study drug, and which does not necessarily have a causal relationship to the study drug.
Baseline	Observed values/findings that are regarded as the observed starting point for comparison. Visit 2 is the Baseline visit in this study.
Discontinuation	The act of an enrolled subject concluding study participation prior to completion of all protocol-required assessments. Data from discontinued subjects are not necessarily excluded from the data analyses.
Endpoint	A variable that pertains to the trial objectives
Enroll	To register or enter into a clinical trial. NOTE: Once a subject has been enrolled, the clinical trial protocol applies to the subject.
Investigational period	Period of time during which protocol objectives are observed, and when the test drug and comparative drug (sometimes without randomization) is given to subjects, and continues until the last assessment after completing administration of the test drug or comparative drug.
Randomization	The process of assigning study subjects to treatment or control groups, using an element of chance to determine treatment assignments, in order to reduce bias.
Screening	A process of active consideration of potential subjects for enrollment in a trial.
Screen failure	A potential subject who did not meet one or more criteria required for participation in the trial.
Screening period	Period of time before the investigational period, from the time of informed consent at Visit 1 until just before the test drug or comparative drug is given to the subject at Visit 2.
Study period	Period of time from the first site's initiation date to the last site's completion date.
Subject	An individual who participates in a clinical study, either as a recipient of the study drug or as a control.
Treatment period	For this study, from randomization at Visit 2 through Visit 5 (Week 12/End of Treatment).
Variable	Any quantity that varies; any attribute, phenomenon, or event that can have different qualitative or quantitative values.

1 INTRODUCTION

This Statistical Analysis Plan (SAP) contains a more technical and detailed elaboration of the principal features of the analysis described in the protocol, and includes detailed procedures for executing the statistical analysis of the primary and secondary endpoints and other data. The SAP is finalized and signed prior to unblinding.

This statistical analysis is coordinated by the responsible biostatistician of Astellas Pharma Inc.. Any changes from the analyses planned in the SAP will be justified in the Clinical Study Report (CSR).

2 FLOW CHART AND VISIT SCHEDULE

Figure 1 Study Design Flow Chart

Study Schematic Diagram

Placebo matched to Mirabegron 50 mg plus Tamsulosin 0.2 mg	Mirabegron 50 mg plus Tamsulosin 0.2 mg
	Placebo matched to Mirabegron 50 mg plus Tamsulosin 0.2 mg

[figure not shown]

Table 1: Schedule of Assessments

	Screening/ Tamsulosin Screening	Treatment Period			
Visit	1	2	3	4	5
Day	-28	1	29	57	85
Week	-4	0	4	8	12
Visit Windows	+/- 7d	-	+/- 7 d	+/- 7 d	+/- 7 d
Visit Windows (Study Days) ^a	-35 to -21	-	22 to 36	50 to 64	78 to 92
Informed Consent	X ^b				
Inclusion/Exclusion Criteria	X	X			
Medical History and OAB History	X				
Demographics	X				
Enter 4-week Tamsulosin Screening ^c	X				
Enrollment	X				
Randomization ^d		X			
Physical Exam	X				
Weight and Height	X				
Vital Signs (includes pulse and blood pressure ^e)	X	X	X	X	X
Serum PSA	X				
Prostate volume	X				
Serum chemistry ^f , hematology ^f , urinalysis	X	X ^d			X
12-Lead ECG (QTcF interval)	X				
Ultrasonography or Bladder Scan (PVR)	X	X	X	X	X
Uroflowmetry ^g	X	X			X
Medication History and OAB Medication History	X				
Concomitant Medications Assessment	X	X	X	X	X
Adverse Event Assessment		X	X	X	X
Dispense Study Drug	X	X	X	X	
Drug Accountability	X	X	X	X	X
Instruct Subject on 3-day Micturition Diary ^h	X	X	X	X	
Subject Completes 3-day Micturition Diary		X ⁱ	X ⁱ	X ⁱ	X ⁱ
OABSS	X	X	X	X	X
IPSS & IPSS (QoL)	X	X	X	X	X

	Screening/ Tamsulosin Screening	Treatment Period			
		2	3	4	5
Visit	1	2	3	4	5
Day	-28	1	29	57	85
Week	-4	0	4	8	12
Visit Windows	+/- 7d	-	+/- 7 d	+/- 7 d	+/- 7 d
Visit Windows (Study Days) ^a	-35 to -21	-	22 to 36	50 to 64	78 to 92
OAB-q	X	X			X
Review Micturition Diary ^j		X	X	X	X

Abbreviations: PSA=Prostate-specific antigen, ECG =electrocardiogram; IPSS = International Prostate Symptom Score; OAB = Overactive bladder; OAB-q = Overactive Bladder questionnaire; OABSS = Overactive Bladder Symptom Score; PVR = Post-void residual (volume); QoL = Quality of Life; UFM = uroflowmetry

- a. Visit windows/study days will be calculated based on Day 1 (Visit 2).
- b. If a drug for the treatment of BPH is to be changed to tamsulosin to enroll a subject in this clinical study, the change to tamsulosin should be done only after informed consent form signature and a new informed consent is to be obtained at Visit 1 (Screening).
- c. Subjects must take tamsulosin for at least 28 days before the Screening period.
- d. Randomization is to occur after confirming all eligibility criteria and after performing all other visit procedures at Visit 2.
- e. Measured during the patient diary period and at each visit (only at visit for discontinued subjects if there is no entry in the patient diary)
- f. Blood samples need not be under fasting conditions.
- g. Any UFM results obtained within 28 days prior to the start of the Screening period may be used, with the subject's consent, instead of the Visit 1 data.
- h. At the Tamsulosin Screening visit (Visit 1), all subjects will be provided a micturition diary that will be used to record the date and time of each of their micturitions, episodes of incontinence, urgency, and voiding volume. Voiding volumes will be collected at Visit 2 (Baseline) and Visit 5 (Week 12). Additionally, the diary will be used to record daily medication intake and self-

measurement of blood pressure and pulse rate. Subjects will be instructed to begin completing the micturition diary 3 days prior to each in-office study visit, including Visit 2 (Baseline) and Visits 3 through 5 (Treatment Period), and to complete the diary for the full 3 days.

- i. For Visits 2, 3, 4, and 5, subjects should complete the micturition diary on the 3 days immediately prior to the study visit, but in any case, on consecutive days within 1 week prior to the study visit.
- j. Investigator, or designee, must review the micturition diary with the subject to ensure completion compliance and to discuss the data captured.

3 STUDY OBJECTIVE(S) AND DESIGN

3.1 Study Objective(s)

The following objectives are investigated in male patients with overactive bladder (OAB) symptoms while taking the alpha blocker, tamsulosin, for benign prostatic hypertrophy (BPH). The hypothesis being tested is that mirabegron is superior to placebo in the treatment of OAB symptoms.

3.1.1 Primary Objective

To study the efficacy of mirabegron versus placebo in male patients with OAB symptoms while taking the alpha blocker, tamsulosin, for BPH.

3.1.2 Secondary Objective

To assess the safety and tolerability of mirabegron versus placebo in male patients with OAB symptoms while taking the alpha blocker, tamsulosin, for BPH.

3.1.3 Other Objectives

To assess patient-reported outcomes as measured by Symptom Bother, and Total Health-Related Quality of Life scores as assessed by the Overactive Bladder questionnaire (OAB-q) and IPSS (QoL) of mirabegron versus placebo in male subjects with OAB symptoms who are taking the alpha blocker, tamsulosin, for BPH.

3.2 Study Design

This is a randomized, double-blind, placebo-controlled study of the efficacy, safety, and tolerability of treatment with mirabegron for OAB in male subjects at least 40 years of age who are taking tamsulosin for BPH. Eligible subjects must have a history of (on average) at least 2 urgency episodes and 8 or more micturitions in a 24-hour period during the 3 days prior to the start of the Screening period.

The study will consist of a 4-week single-blind Screening period followed by a 12-week double-blind Treatment period. During the Screening period and beginning with Visit 1, all subjects will receive tamsulosin 0.2 mg along with mirabegron 50 mg matching placebo once daily after breakfast.

At the conclusion of the 4-week tamsulosin Screening period, subjects will complete a 3-day micturition diary just prior to Visit 2 (Baseline). Subjects who meet entry criteria at the end of the tamsulosin Screening period will be randomized (at Visit 2) to receive either mirabegron 50 mg or matching placebo for 12 weeks of double-blind treatment, while continuing their treatment with tamsulosin 0.2 mg daily.

For randomization, key efficacy assessments, safety and tolerability assessments of mirabegron administered concomitantly with tamsulosin, refer to section [3.3](#), [6.1](#) and [6.2](#) respectively.

Individual subject participation in the study will be ~16 weeks, which includes the 4-week Screening period and the 12-week double-blind Treatment period.

The study will be conducted in Japan (~50 centers) and Korea (~5 centers). The target enrollment is 550 subjects, with 275 randomized to each treatment group.

3.3 Randomization

Subjects will be randomized 1:1 to receive mirabegron 50 mg or matching placebo once daily during the 12-week treatment period. The randomization will be stratified by site.

Randomization will be performed via Interactive Response Technology (IRT). Prior to the initiation of the study treatment, the site staff will contact the IRT in order to determine the randomly assigned treatment for each subject.

4 SAMPLE SIZE

The sample size for this study was based on 248 subjects per treatment group (using the Full Analysis Set [FAS]) to provide 90% power to detect a 0.7 reduction in the mean number of micturitions/24 hours in the mirabegron group compared to the placebo group, at a two-sided alpha level of 0.05. A standard deviation (SD) of 2.4 is assumed.

Assumptions for the mean reduction and SD are based on data from previous studies. If 90% of the randomized subjects are evaluable for efficacy, 550 subjects should be randomized, with 275 subjects randomized to each treatment group.

5 ANALYSIS SETS

In accordance with International Conference on Harmonization (ICH) recommendations in guidelines E3 and E9, the following analysis sets will be used for the analyses.

The final handling of the analysis sets will be decided with the decisions based on the opinions and advice of medical experts prior to breaking of the randomization code.

Demographics and other baseline characteristics will be summarized by treatment group for the Full Analysis Set, Per Protocol Set (PPS), and Safety Analysis Set (SAF).

The efficacy analysis will be conducted on the FAS, with the PPS as a supportive analysis.

All secondary efficacy analyses will be performed on the FAS.

The safety analysis will be performed on the SAF.

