The primary analysis set is the FAS, which will include all subjects who meet the following criteria:

- Those who took at least one dose of double-blind study medication after randomization
- Those who had a micturition measurement in the Baseline visit diary and at least one micturition measurement in the post- Baseline visit diary

Subjects who are included in the FAS and who meet all of the following criteria will be included in the Per Protocol Set (PPS):

- Those subjects who did not violate the inclusion or exclusion criteria
- Those subjects with no less than 80% drug compliance during the Screening and Treatment period
- Those subjects who took the study drug for at least 42 days during the Treatment period, from the day following dispensing. However, any subjects who discontinued the study for efficacy-related reasons, such as insufficient therapeutic effect, will be included in the PPS, even if the drug was taken for fewer than 42 days.
- Those subjects whose diary was completed for at least 2 of the 3 consecutive days for Visit 2 and the last visit during the Treatment period.
- Those subjects who did not receive any of the prohibited concomitant medications/therapies that could affect the evaluation of efficacy.

The End-of-Treatment assessment will be analyzed to account for subjects who prematurely discontinued from the study. The End-of-Treatment assessment is defined as the last post-Baseline visit assessment during the double-blind study period for which data for the primary efficacy variable is available.

Continuous variables will be summarized using descriptive statistics (i.e., mean, SD, minimum, median, Quartile 1 [Q1], Q3, and maximum). Categorical variables will be described using absolute and relative frequency.

The primary efficacy variable is the change from Baseline to End-of-Treatment in the mean number of micturitions/24 hours, based on the 3-day micturition diary. It will be analyzed using an Analysis of Covariance (ANCOVA), including treatment group and region as fixed factors and baseline as a covariate. Within the framework of the ANCOVA model, point estimates and two-sided 95% confidence intervals for the mean change from Baseline within each treatment group, as well as for the difference in mean change from Baseline between the mirabegron treatment group and placebo, will be calculated.

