5.3 Efficacy Assessments

5.3.1 Micturition Diary

The micturition diary will be used to record the date and time of each micturition, incontinence episodes, urgency episodes, and voiding volume. Voiding volume will be recorded at Visits 2, and 5 only. The diary will also be used to record daily medication intake. The diary must be completed for at least 2 days in order to be included in the efficacy assessment for that visit.

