6 DISCONTINUATION

6.1 Discontinuation of Individual Subject(s)

A discontinuation is a subject enrolled in the study for whom study treatment is prematurely discontinued, for any reason.

The subject is free to withdraw from study treatment and/or the study for any reason and at any time without giving reason for doing so and without penalty or prejudice. The Investigator is also free to terminate a subject's involvement in the study at any time if the subject's clinical condition warrants it.

If a subject is discontinued from the study and has an ongoing AE or an unresolved laboratory result that is significantly outside of the reference range, the Investigator will attempt to provide follow-up until the condition stabilizes or is no longer clinically significant.

Treatment Discontinuation Criteria for Individual Subjects:

- Due to an AE
 - When continuation in the study is judged to be difficult due to development of an AE or SAE
 - When continuation in the study is judged to be difficult due to aggravation of a concurrent disease requiring a change in treatment from the protocol
- Lack of efficacy
- Withdrawn consent
- Lost to follow-up
- Deviation from the inclusion or exclusion criteria during the Screening period
- Protocol deviations
 - When a subject is found not to have met the inclusion criteria at enrollment, or to have met the exclusion criteria after enrollment and therefore, was determined to be ineligible for the study
 - Any other serious violation of the protocol
- Other
 - When the Investigator judges that the subject must be withdrawn from the study, for any reason.

For those subjects who are withdrawn from the study after study drug administration, the examinations and evaluations scheduled for the final visit of the treatment period will be performed at the time of discontinuation, as much as possible (See Section V, Figure 1 Study Design Flow Chart and Table 1 Schedule of Assessments). If the subject is discontinued due to an AE, appropriate treatment will be provided, as necessary.

The Investigator will record the date and reason for the subject discontinuation and enter in the eCRF.

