5.1 Full Analysis Set (FAS)

The FAS consists of all subjects who are randomized and receive at least 1 dose of double-blind study drug and have a Baseline micturition measurement and at least 1 post-Baseline micturition measurement.

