Completed at Visit 2	1	-
Completed at Visit 3	29	Day 22 to Day 36
Completed at Visit 4	57	Day 50 to Day 64
Completed at Visit 5	85	Day 78 to Day 92
Questionnaires are to be completed at the final evaluation during the Treatment period.	Final diary must be completed within 7 days after the last dose of study drug.	

*OAB-q not performed at Visit 3 and Visit 4.

Safety Assessments

The time windows for the analysis of residual urine volume, laboratory tests*, and measurement of blood pressure (BP) and pulse rate (PR) are described below:

Time Point for Evaluation	Scheduled Day	Acceptable Time Range
Visit 1	-28	Day -35 to Day -21
Visit 2	1	-
Visit 3	29	Day 22 to Day 36
Visit 4	57	Day 50 to Day 64
Visit 5	85	Day 78 to Day 92
Final evaluation during the Treatment period	Final evaluation must be performed within 7 days after the last dose of study drug.	

* Performed only at Week -4, Week 0, and Week 12/early termination

The time windows for the analysis of self-measurement of BP and PR are described below:

Time point	Scheduled day	Acceptable time range
Diary retrieved at Visit 2	1	Day -7 to Day -1
Diary retrieved at Visit 3	29	Day 19 to Day 35
Diary retrieved at Visit 4	57	Day 47 to Day 63
Diary retrieved at Visit 5	85	Day 75 to Day 91
The diary is to be retrieved at the final evaluation during the Treatment period.	The final diary must be completed within 7 days after the last dose of study drug.	

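### OABSS, IPSS and OAB-q are analysed on a diary-based FAS with a diary-based End of Treatment, so some questionnaires completed at discontinuation are left out

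*SAP*

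**What the plan says.** **Analysis set.** SAP 5 says "All secondary efficacy analyses will be performed on the FAS", with the PPS, a subset of the FAS, as support. Under SAP 7.4.2, the change to End of Treatment in OABSS, IPSS and the two main OAB-q scores is compared by ANCOVA on the FAS and PPS. SAP 7.4.3 summarises the OAB-q subscales on the FAS.

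**Entry to the FAS.** Under SAP 5.1, randomised and dosed men must "have a Baseline micturition measurement and at least 1 post-Baseline micturition measurement". The protocol synopsis names the source: "at least one micturition measurement in the post- Baseline visit diary". Protocol 5.3.1 sets the minimum: "The diary must be completed for at least 2 days in order to be included in the efficacy assessment for that visit".

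**End of Treatment.** SAP 7.1 gives one definition for all endpoints: the last post-baseline double-blind assessment with data on the primary variable, which is the diary count.

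**Questionnaires at discontinuation.** Protocol 6.1 says that for men withdrawn after study drug, the final-visit assessments "will be performed at the time of discontinuation, as much as possible". All three questionnaires are on the Visit 5 list in Table 1. SAP 7.10.3 adds: "Questionnaires are to be completed at the final evaluation during the Treatment period". The same section allows a final diary within 7 days after the last dose.

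**No separate provision.** Neither document defines a questionnaire-specific set, a questionnaire-specific End of Treatment or a sensitivity analysis that would use these data.

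**The concern.** A questionnaire is answered at the visit, whereas the diary has to be kept at home on the days before it. Under Protocol 5.1.5 the site writes the diary dates in advance for the next scheduled visit. A man who stops early and comes in unscheduled can therefore give a complete OABSS, IPSS and OAB-q without a usable diary. Footnote e to SAP Table 1 concerns home blood pressure and pulse, but these are recorded in the same diary. It foresees such men, since it has vital signs taken "only at visit for discontinued subjects if there is no entry in the patient diary".

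For the questionnaire endpoints, the rule discards an observed outcome because a different instrument is missing after randomisation. Adverse events and lack of efficacy are among the discontinuation reasons in Protocol 6.1, and either could differ by arm. Patient-reported outcomes are a named objective in SAP 3.1.3. At stake are some precision and some avoidable post-randomisation selection in secondary and exploratory comparisons.

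**Working it through.** **1. The plan's own figures.** From SAP 4: difference 0.7, SD 2.4, two-sided alpha 0.05, power 90%, 90% evaluable.

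- n per arm = 2 × [2.4 × (1.960 + 1.2816) / 0.7]² = 247.03, rounded up to 248. This matches the plan; power at 248 is 90.1%.
- 248 / 0.9 = 275.6, against 275 randomised per arm (275 × 0.9 = 247.5). This agrees to within rounding.

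**2. Who is affected.**

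| Man | In the FAS? | Discontinuation questionnaire used? |
|---|---|---|
| Dosed, no usable post-baseline diary, questionnaires at discontinuation | No | No, for all three instruments |
| Usable Week 4 or 8 diary, then leaves with questionnaires but no diary | Yes | Read literally, no: OABSS and IPSS fall back to the earlier visit, and OAB-q has no value there |
| Leaves with questionnaires and a usable diary within 7 days of the last dose | Yes | Yes |
| Randomised, never dosed | No | Not applicable; still excluded under the fix |

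The first row follows from SAP 5 and 5.1, the second from SAP 7.1. Changing the set alone would not help the first group: with no diary they have no End of Treatment assessment, and SAP 7.10.1 does not impute efficacy data.

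**3. Ceiling on the men outside the FAS.** 550 × 0.10 = 55, or 275 − 248 = 27 per arm. The allowance covers everyone not evaluable, including undosed men and men with neither instrument. The recoverable number is therefore somewhere from 0 to below this ceiling.

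**4. Precision.** With k men per arm recovered, SE ratio = √[248 / (248 + k)].

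| k per arm (assumed) | n per arm | SE ratio |
|---|---|---|
| 0 | 248 | 1.000 |
| 7 | 255 | 0.986 |
| 14 | 262 | 0.973 |
| 20 | 268 | 0.962 |
| 27 (ceiling) | 275 | 0.950 |

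On totals, √(495/550) = 0.949. The gain is thus 0 to about 5%.

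**5. Bias, illustration only.** Let p be the share of an arm dropped with a questionnaire, and let dropped men improve d points less, with the same d in both arms. Each arm's mean change then moves by p × d, and the mirabegron-minus-placebo difference moves by d × (p_mirabegron − p_placebo) when they are restored. All of these values are assumptions:

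- d = 2 OABSS points, 4% on mirabegron and 8% on placebo: 2 × (0.04 − 0.08) = −0.08.
- Equal shares: 0.
- Shares swapped: +0.08.

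For scale, the open-label randomised study in Protocol 1.2 gives −2.21 − (−0.87) = −1.34 on OABSS, and 0.08 / 1.34 = 6%.

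**The case against.** **Collection is not guaranteed.** Protocol 6.1 asks for the final assessments only as far as possible, and a final diary is expected at the same point. Only men who supply the questionnaire without the diary matter, and footnote e does not show that such men completed questionnaires. This stands, and it is why the count may be near zero.

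**A common population has merit, and early values are hard to read.** The IPSS asks about the past month (Protocol 12.4), so an IPSS in the first weeks of treatment partly describes the Screening period. Calling it End of Treatment is an arguable choice. This also stands, as a downside to weigh. A common denominator is already given up, because the nocturia and incontinence analyses use their own subsets.

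**The sets can be settled before unblinding.** SAP 5 allows this on expert advice but gives no rule that would admit these men. A written rule is better than a late decision.

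**Stronger readings to avoid.** A reader might infer that the plan discards questionnaires from 55 men. The documents do not support this: the 10% is a planning allowance for all non-evaluable men and can include undosed ones. A reader might also infer that the rule favours mirabegron. No arm-specific loss or reason is given, and the illustration changes sign with the assumption.

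**Conclusion.** The point holds on the text. The diary-based FAS and the diary-based End of Treatment together exclude questionnaire outcomes that the protocol plans to collect, and nothing in either document recovers them. OAB-q is the most exposed, with one scheduled post-baseline visit.

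The size is modest and uncertain. The number of men is not in the documents. The standard error would fall by 0 to at most about 5%, and the upper end needs every non-evaluable man to be dosed and to have a questionnaire, which is not realistic. Any bias has unknown direction, and the 0.08-point figure rests wholly on assumed loss rates and an assumed deficit. Only secondary and exploratory endpoints are touched. The primary analysis and the 248/275 sample size are unaffected, because the primary endpoint is the diary itself. It is a worthwhile, inexpensive improvement and no threat to the trial's main conclusion.

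**What to change.** Keep the FAS for diary endpoints. For OABSS, IPSS with its QoL item, and OAB-q, amend SAP 5, 7.1 and 7.4.2, and also 7.4.3 for the OAB-q subscales:

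- **Set:** all randomised men with at least one double-blind dose, a baseline value and at least one post-baseline value of that questionnaire, by assigned arm.
- **End of Treatment:** the last post-baseline value of that questionnaire within 7 days after the last dose.
- **Model:** the same ANCOVA where one is planned.
- **Reporting:** by arm, the number of men with a post-baseline questionnaire but no post-baseline diary.

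Both definitions must change, for the reason given in step 2 of the working. If the sponsor prefers to keep the FAS as the main set, add this as a sensitivity analysis at minimum.

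The cost is SAP wording and extra population and End of Treatment flags, with no new data collection. Protocol 7.2.1 and 7.4.2 place the secondary endpoints on the FAS, so the change must be declared as a departure from the protocol. Denominators will differ between questionnaire and diary endpoints, and the report should note that early IPSS values partly recall the Screening period.
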